Statistical Methods and Planned Analyses:	
Populations:
 
Safety analysis set: All randomized subjects who receive at least 1 dose of study medication. The Safety Analysis Set will be used primarily for the analysis of safety data. Subjects will be classified based upon the treatment received.
 
Full analysis set (FAS): All randomized subjects who receive at least 1 dose of study medication, who underwent an elective BR surgery as specified in the protocol, and who provided at least 1 post-surgery assessment of the primary endpoint (GIR) during the treatment period. The FAS will be used primarily for the analysis of efficacy data. Participants will be analyzed according to the treatment group to which they are randomized.
 
Per-protocol analysis (PP) set: A subset of the FAS who:
 
 Had a protocol-specified surgery Did not take prohibited medications during the treatment period that could affect the primary endpoint Had otherwise complied with the protocol without any other major protocol deviation (any exceptions for inclusion/exclusion criteria granted by the Sponsor/medical monitor will not be considered protocol violations) 
PK analysis set: All subjects who have PK data available for at least 1 dose of TU-100.
 
The primary efficacy variable is time to TGIR, a composite endpoint defined as the following: $\text{TGIR} = \text{maximum}(\text{time to first toleration of liquids; time to first BM OR [absence of distention AND bowel sounds AND flatus]})$
 
Time to an event is defined as the elapsed time, in hours, from the end of surgery to the time of the first event, to be calculated as:
 $\text{Time to event (hours)} = (\text{time of the event} - \text{time of end of surgery})$ 
The primary analysis of TGIR will be based on the Cox proportional hazard model (Cox PH) that includes the main effects for treatment and surgical approach (open versus laparoscopic). The estimates of time to event for the quartiles (25%, 50%, 75%), hazard ratios and their corresponding one-sided 95% confidence intervals (CIs), the Wald Chi-square one-sided P values from the Cox analysis will be summarized. The ties in the data will be handled by the Breslow method.
 
A secondary analysis will be applied for TGIR using the Cox PH model including main effects for treatment, surgical approach (open versus laparoscopic), and covariates such as surgical type, gender, age (years), post-operation opioid consumption (mg morphine equivalents), thoracic epidural use, and surgery duration (hours). Backward method will be used to select statistically significant covariates ($P < 0.1$). Adjusted P value and hazard ratio (HR) will be provided after the final model is selected.
 
In addition, TGIR will be assessed for TU-100 versus placebo at each dose level using a stratified log-rank with the one stratum used for randomization: surgical approach (open versus laparoscopic). The Kaplan-Meier estimate of the median TGIR and the corresponding 1-sided 95% CIs calculated using the Greenwood's formula will be presented. Plot of the Kaplan-Meier estimate of the survival distribution function over time will be presented. The restricted mean survival time (RMST) at time t^* using the Kaplan-Meier estimate of the survival function will also be provided, where t^* is the minimum of the largest observed time (event or censored) in each of the 2 groups. Furthermore, the difference in RMST, as well as the ratio of RMST between 2 groups will be evaluated. Similar analyses will be applied for other time to event efficacy endpoints.
 
A secondary efficacy variable, time to ready for discharge (based solely on the treating medical team's determination of GI recovery), which is defined as the time to the assessment date of "ready for hospital discharge." Length of stay is based on the time to the calendar day of discharge order written from the calendar day of surgery.
 
Treatment effect on other numeric variables will be analyzed using an analysis of variance (ANOVA) if normally distributed, or the Wilcoxon rank sum test otherwise. Treatment effect on categorical variables will be analyzed using the stratified Miettinen and Nurminen (M&N) method (stratified by surgical approach), or the logistic regression model if appropriate.

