7 INVESTIGATIONAL PLAN

7.1 Description of Overall Study Design and Plan

This multicenter, randomized, double-blinded, placebo-controlled study will evaluate the effect of TU-100 on resolution of POI in subjects undergoing open or minimally invasive BR. Straight, hand-assisted, and robotically-assisted laparoscopic approaches are allowed. Subjects undergoing major abdominal resective intestinal surgeries (BRs; e.g., small BR, large BR, rectal resections [low anterior resection], total colectomy with ileo-rectal anastomosis) will be eligible for enrollment.

Subjects will be screened up to 28 days before their planned surgery and will be randomized 1:1:1 (TU-100 15 g/day: TU-100 7.5 g/day: placebo) on postoperative Day 1 before the first dose of study medication. Subjects will be stratified based on surgical approach (open versus laparoscopic). After randomization, subjects will receive a total daily dose of TU-100 15 g, TU-100 7.5 g, or matching placebo TID until hospital discharge or \leq 10 days (whichever is earlier). All subjects will be treated with study medication as adjunct to an enhanced recovery (i.e., ERAS) pathway for GI recovery, the components of which are standardized, to the extent possible, by the protocol (SOC) (See [Section 7.2](#)).

Efforts will be made to obtain 134 subjects in each of the 3 treatment groups for a total of 402 subjects.

[figure not shown]
There will be 2 independent committees with additional safety oversight. Each will have a formal charter and their specific roles will be discussed within this protocol.

- Data and safety monitoring board (DSMB; clinical trial safety oversight)
- Clinical endpoint adjudication committee (CEAC; for assessment of hepatobiliary AEs)

This study follows the FDA guidance on the conduct of clinical trials and statistical considerations for clinical trials during the COVID-19 pandemic as necessary.

[Figure 1](#) presents the study design.

Figure 1. Study Design

- Abbreviations: R = Randomized; S = Surgery.
- ^a Treatment will be for a maximum of 10 days while subjects are hospitalized. If a subject is discharged before postoperative Day 10, study medication will be discontinued upon hospital discharge.

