10.2.1.3 Postoperative Elements

- A multimodal, opioid-sparing, pain management plan should be implemented as appropriate (e.g., combination of acetaminophen and NSAIDs).
 - Gabapentinoids (i.e., gabapentin, pregabalin) should not be used unless indicated for postoperative neuropathic pain. (See [Section 9.6.1](#))
 - **Note:** although an opioid-sparing approach should be used for postoperative pain management, opioid analgesics use is not prohibited.
- Indwelling NGTs for *prophylaxis* cannot be used.
- Protocol guidelines for selective postoperative nasogastric intubation for the management of clinical events should be followed, as shown below.
 - Occurrence of one or more of the following events:
 - ≥ 2 low-volume (e.g., < 300 cc) episodes of emesis
 - ≥ 1 high-volume (e.g., ≥ 300 cc) episode of emesis
 - Moderate to severe abdominal distension
- IV fluids are to be discontinued as soon as the subject can tolerate oral liquids and maintain adequate hydration.

- Begin oral feeding early unless otherwise contraindicated.
- Subjects must be mobilized early, starting from Day 1 unless otherwise contraindicated.
- For the purposes of this protocol, in order to reduce confounding of the effect of TU-100 on the primary outcome measure, the following interventions are prohibited:
 - Alvimopan, methylnaltrexone, naloxone (except for treatment of known or suspected opioid overdose)
 - Routine use of laxatives and stool softeners
 - Prophylactic use of prokinetics (e.g., metoclopramide, cisapride, domperidone, erythromycin used as a prokinetic agent)
 - Sham feeding (e.g., gum chewing)

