11.6 Time to Transition of Oral Analgesics

The time when the subject is able to transition from IV to oral analgesics should be noted on the eCRF by the investigator.

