14 STATISTICAL ANALYSIS

14.1 General Considerations

A statistical analysis plan (SAP) will be prepared after the protocol is approved. This document will provide further details regarding the definition of analysis variables and analysis methodology to address all study objectives. The SAP will serve as a compliment to the protocol and supersedes it in case of differences.

The statistical evaluation will be performed using Statistical Analysis Software (SAS)[®] version 9.4 or higher (SAS Institute, Cary, NC). All summaries will be presented by cohort and overall for each part, when appropriate. Summary statistics will be presented by dose group. For continuous variables, data will be summarized with the number of subjects (N), mean, standard deviation, median, minimum, and maximum by treatment group. For categorical variables, data will be tabulated with the number and proportion of subjects for each category by treatment group.

The precision of the measurement units for each continuous variable will be used to determine the number of decimal places used to report these summary statistics. Minimum and maximum values will be reported with the same precision as the units of measure. The mean and median will be reported to 1 greater decimal place, and the standard deviation will be reported to 2 additional decimal places. Any values that require transformation to standard units (metric or international [SI]) will be converted with the appropriate corresponding precision. Percentages will be presented to 1 decimal place. For statistical analyses, baseline is defined as the most recent measurement before initiation of first study drug administration.

The SAP will provide specific details on the analytical methods and data displays. Any change to the data analysis methods described in the protocol will require an amendment ONLY if it changes a principal feature of the protocol. Any other change to the data analysis methods described in the protocol, and the justification for making the change, will be described in the CSR. Additional exploratory analyses of the data will be conducted as deemed appropriate.

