14.2 Determination of Sample Size

The study is expected to enroll approximately 402 eligible subjects (with expected loss to follow-up or censorship of primary endpoint) with 1:1:1 randomization ratio over a post-surgery period (up to 10 days). The study is sized to achieve approximately 87% power to detect a hazard ratio (HR; TU-100 versus placebo) of 1.428 for GIR, which translates into an improvement in median time to GIR from 48 hours (2.0 days) for placebo (reference) to 34 hours (1.4 days) for TU-100 at a 0.05 significance level of one-sided log-ranked test for equality of time to GIR survival curve.

Based on historical evidence, it is assumed that a small proportion of subjects will be lost to follow-up or will have events censored due to required analytical methods. To account for this anticipated loss in contribution of events to the primary endpoint, an additional 36 subjects (approximately 10% of 366) will be enrolled to achieve a final sample size of 402 subjects (134 per group).

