14.5.2 Analysis of Primary Efficacy Endpoint

The primary efficacy variable is time to gastrointestinal recovery (TGIR), a composite endpoint defined as the following:

TGIR = maximum (time to first toleration of liquids; time to first BM OR [absence of distention AND bowel sounds AND flatus])

Time to an event is defined as the elapsed time, in hours, from the end of surgery to the time of the first event, to be calculated as:

$$\text{Time to event (hours)} = (\text{time of the event} - \text{time of end of surgery})$$

When TGIR is greater than 10 days (240 hours), it will be censored at 10 days. Censoring rules for other secondary time-event endpoints will be discussed in the SAP.

The primary analysis of TGIR will be based on the Cox proportional hazard model (Cox PH) that includes the main effects for treatment and surgical approach (open versus laparoscopic). The estimates of time to event for the quartiles (25%, 50%, 75%), hazard ratios and their corresponding one-sided 95% confidence intervals (CIs), the Wald Chi-square one-sided *P* values from the Cox analysis will be summarized. The ties in the data will be handled by the Breslow method.

A secondary analysis will be applied for TGIR using the Cox PH model including main effects for treatment, surgical approach (open versus laparoscopic), and covariates such as surgical type, gender, age (years), post-operation opioid consumption (mg morphine equivalents; [APPENDIX 2](#)), thoracic epidural use, and surgery duration (hours). Backward method will be used to select statistically significant covariates (*P* < 0.1). Adjusted *P* value and HR will be provided after the final model is selected.

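### The adjusted Cox model for time to GI recovery includes postoperative opioid use with no time window, so it takes in use after randomisation and can bias the adjusted hazard ratio

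*Combined protocol and SAP*

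**What the plan says.** Section 14.5.2 follows the primary Cox model (treatment and surgical approach only) with a secondary model for time to GI recovery (TGIR). Its candidate covariates are introduced as "covariates such as surgical type, gender, age (years), post-operation opioid consumption (mg morphine equivalents", with a pointer to Appendix 2, and the synopsis has the same item: "post-operation opioid consumption (mg morphine equivalents), thoracic epidural use, and surgery duration (hours". On selection, "Backward method will be used to select statistically significant covariates" at P < 0.1, and the adjusted hazard ratio (HR) and P value from the selected model are to be reported. Section 14.6.3 summarises the same opioid variable descriptively, again with no window.

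Three other provisions bear on the timing:

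- Section 14.5.2 measures TGIR from the end of surgery, but Section 7.1 places randomisation "on postoperative Day 1 before the first dose of study medication".
- Section 10.2.1.3 keeps opioids available after surgery: "although an opioid-sparing approach should be used for postoperative pain management, opioid analgesics use is not prohibited".
- Section 11.6 expects intravenous analgesia to give way to oral: "The time when the subject is able to transition from IV to oral analgesics should be noted on the eCRF".

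Section 14.1 leaves detail to the SAP: "This document will provide further details regarding the definition of analysis variables and analysis methodology". No supplied text sets the window. Section 17 describes Appendix 2 only as an opioid conversion chart. The appendix itself is not in the supplied text, and its absence is not held against the plan.

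**The concern.** A covariate in a model that estimates a treatment effect should be fixed before treatment starts. Surgical type, gender, age and surgery duration are. Opioid use without a window is not, and it can go wrong in two ways, each conditional on something the documents do not state.

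1. **Accrual.** The unit is mg morphine equivalents with no per-day denominator, which fits a total. If the total runs until recovery or discharge, a subject who recovers later has more time to accumulate opioid. The covariate then carries part of the outcome, and adjusting for it removes part of a real treatment effect.
2. **Effect of treatment on opioid use.** If the drug raises or lowers opioid use, the model conditions on a consequence of treatment, and the HR can move either way.

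Backward selection offers little protection, because a covariate that tracks the outcome tends to be kept. At stake is a reported adjusted HR and P value that could make a true effect seem to fade, or misstate it, in a table read beside the primary result.

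**Working it through.** **Sizing figure.** Section 14.2 states: "The study is sized to achieve approximately 87% power to detect a hazard ratio" of 1.428, one-sided 0.05. Before inflation there are 366/3 = 122 subjects per arm. Counting all as events, each dose-versus-placebo comparison has d = 244. Schoenfeld with 1:1 allocation:

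power = Φ(√d × ln HR / 2 − 1.645) = Φ(15.62 × 0.3563 / 2 − 1.645) = Φ(1.138) = 87.2%.

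This reproduces the stated 87%. The documents give no figure for the adjusted model.

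**Simulation.** From the plan: 122 per arm, HR 1.428 or 1, censoring at 240 h, covariate kept at P < 0.1, one-sided 0.05 Wald test. Assumed:

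- Randomisation is uniform 12–28 h after surgery. Time from randomisation to recovery is exponential, with placebo median 28 h.
- Surgical approach is 50:50 with log-HR 0.25. Discharge is 6–24 h after recovery.
- The opioid rate is lognormal with CV 0.3, 0.5 or 0.8, and is constant or falls with a 36-h or 18-h half-life.
- Pain either does not affect recovery or lowers its log hazard by 0.3 per SD.

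That makes 18 opioid patterns, with 3,000 trials per setting. The placebo median is about 20 + 28 = 48 h from surgery, as in the plan. The drug-arm median is about 20 + 28/1.428 = 39.6 h, against 34 h in Section 14.2.

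**True HR 1.428, adjusted for total to discharge** (entries for CV 0.3 / 0.5 / 0.8):

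| Pain slows recovery? | Opioid rate | Adjusted HR | Power, % | Covariate kept, % |
|---|---|---|---|---|
| No | constant | 1.21 / 1.29 / 1.36 | 42 / 61 / 74 | 100 |
| No | 36-h half-life | 1.36 / 1.40 / 1.42 | 74 / 81 / 84 | 95–100 |
| No | 18-h half-life | 1.42 / 1.43 / 1.43 | 83 / 85 / 86 | 99 / 73 / 39 |
| Yes | constant | 1.30 / 1.35 / 1.38 | 62 / 72 / 78 | 100 |
| Yes | 36-h half-life | 1.40 / 1.42 / 1.43 | 79 / 83 / 84 | 95–100 |
| Yes | 18-h half-life | 1.43–1.44 | 84–85 | 100 |

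Without opioid adjustment the HR is 1.43 (power 86%) when pain has no effect on recovery and 1.39 (82%) when it has.

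**Other definitions, same trials, all 18 patterns:**

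| Definition | HR | Power, % |
|---|---|---|
| Dose before randomisation | 1.43–1.44 | 86–87 |
| First 48 h | 1.43–1.44 | 85–86 |
| First 72 h | 1.39–1.44 | 77–86 |
| Per-day average | 1.20–1.43 | 39–86 |

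Under the 18-h taper the per-day average still gives 1.20–1.39 (39–80%), so a fast taper does not rescue that definition.

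**No treatment effect on recovery, total to discharge.** With equal opioid use in both arms the HR is 1.00 and rejection 5–8%, against 5% unadjusted. With an assumed 15% lower opioid rate on drug after randomisation, the HR is 0.73–1.00 and rejection 0–6%. With a 15% higher rate, the HR is 1.01–1.34 and rejection 6.5–70%. Under the same shifts, the unadjusted and pre-randomisation models both give HR 1.00 and 6% (1,500 trials per setting).

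**Second simulation, different assumptions** (randomisation at 18 h, placebo median 30 h later, constant rate, pain slows recovery, 1,000 trials per setting). At true HR 1.428 a total to recovery gave 1.33 with 68% rejection, against 1.43 and 86% for dose before randomisation. A total to discharge gave 1.36 and 73%. With no treatment effect on recovery, opioid-rate ratios of 0.82 and 1.22 moved the HR for a total to recovery to 0.83 and 1.21. The directions agree.

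**The case against.** The strongest reply is that this is an undefined variable, not a faulty model. Section 14.1 assigns definitions to the SAP, which supersedes the protocol; the covariate list is illustrative; and the model is secondary, with nominal P values and no decision attached. All of that stands, and it limits the consequence. It does not supply the window.

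A second objection is that the largest losses need a near-constant opioid rate until discharge. That fits poorly with an opioid-sparing plan and an expected switch to oral analgesics. This also stands: with an 18-h half-life a total does almost no harm. Likewise, the documents give no evidence that the drug changes opioid use.

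A third is that the direction is not fixed. When pain slows recovery and opioid use tapers, adjusting for the total raises the HR from 1.39 to 1.40–1.44. That is true against the unadjusted model, whose HR is low because it omits a prognostic factor. The better comparison is with the pre-randomisation dose, which captures the same factor. With equal opioid use in both arms, the total never exceeded that benchmark.

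Finally, a fixed 48-h window performs nearly as well as the pre-randomisation dose. It does remove the accrual problem, but it stays open to bias if treatment changes opioid use: in the second simulation a rate ratio of 0.82 gave HR 0.93 with a true HR of 1. The 40 h versus 34 h drug-arm median does not change the mechanism.

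**Conclusion.** The concern holds. As written, the covariate includes opioid use after randomisation, and nothing supplied restricts it. With a working drug and a total growing at a near-constant rate, the adjusted HR is pulled toward 1: from 1.428 to between 1.21 and 1.38 in the simulated patterns. With a fast taper a total is almost harmless. If treatment changes opioid use, the error can go either way. If treatment affects neither recovery nor opioid use, the HR is unbiased and rejection is 5–8%.

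The mechanism and its direction are supported. The sizes are not estimates for this trial, because every opioid pattern is assumed. The reach is one secondary model; the primary Cox model, stratified log-rank test, Kaplan-Meier and RMST analyses are unaffected. Section 14.5.3 applies similar analysis to the other time-to-event endpoints, so the covariate might also enter those models, but the wording does not settle that. The point should be corrected before unblinding, since a window chosen later would be open to the data.

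**What to change.** Define the covariate in the SAP, and align Section 14.5.2 and the synopsis, as *opioid dose (mg morphine equivalents) from end of surgery to randomisation*. If dose times are not captured, drop opioid use from the adjusted model. Summarise post-randomisation use by arm, which extends the descriptive summary already planned in Section 14.6.3. If a fixed window running past randomisation is kept, such as the first 48 h, prespecify it before unblinding and label that model exploratory.

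The cost is a wording change and possibly a small eCRF addition. Section 9.6.1 has medications before study drug recorded and allows for more opioid detail, but does not promise dose times. Dropping the covariate needs no new data. Section 14.1 requires a protocol amendment only when a principal feature changes, so the SAP definition could come first.

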In addition, TGIR will be assessed for TU-100 versus placebo at each dose level using a stratified log-rank with the one stratum used for randomization: surgical approach (open versus laparoscopic). The Kaplan-Meier estimate of the median TGIR and the corresponding 1-sided 95% CIs calculated using the Greenwood's formula will be presented. Plot of the Kaplan-Meier estimate of the survival distribution function over time will be presented. The restricted mean survival time (RMST) ([Uno 2015](#)) at time t^* using the Kaplan-Meier estimate of the survival function will also be provided, where t^* is the minimum of the largest observed time (event or censored) in each of the 2 groups. Furthermore, the difference in RMST, as well as the ratio of RMST between 2 groups will be evaluated. Similar analyses will be applied for other time to event efficacy endpoints.

The effect of some additional potential covariates on treatment effect may also be evaluated using appropriate methods. Sensitivity analyses for TGIR will be described in the SAP.

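### The RMST horizon for TGIR is taken from the data separately for each dose, so the two RMST differences may cover different windows and may drop late placebo time, although a 240 h limit is already in the plan

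*Combined protocol and SAP*

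**What the plan says.** Section 14.5.2 makes a Cox model the primary analysis of TGIR and adds supportive analyses. Among these, "TGIR will be assessed for TU-100 versus placebo at each dose level using a stratified log-rank". RMST is then estimated from the Kaplan-Meier curves up to a time t*, which "is the minimum of the largest observed time (event or censored) in each of the 2 groups", and "the difference in RMST, as well as the ratio of RMST between 2 groups will be evaluated". The Synopsis (Statistical Methods) repeats the definition. Neither place requires the two dose comparisons to share a t*.

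The same section fixes an upper limit for the endpoint: "When TGIR is greater than 10 days (240 hours), it will be censored at 10 days". That caps t* at 240 h but does not set it there. The supportive analyses are extended to the other time-to-event endpoints, for which no limit is given: "Censoring rules for other secondary time-event endpoints will be discussed in the SAP".

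**The concern.** An RMST difference has a meaning only together with its horizon. Under this rule the horizon is a random quantity that depends on how fast the arms recover, and it is determined once for 15 g versus placebo and again for 7.5 g versus placebo. A table with the two differences side by side may then report hours saved over, say, 140 h for one dose and 165 h for the other.

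The direction also matters. If every subject in the active arm has recovered by some time before 240 h, t* is that arm's last recovery time, and any placebo subject still unrecovered stops contributing there. The dropped time lies in the slow-recovery tail. That tail is of interest here: prolonged ileus is a listed outcome (Sections 6.2.4 and 11.7), and the rationale in Section 5.4 points to benefit in patients thought to have ileus. At stake is how well a supportive estimate is defined and how easily the two doses can be read together, not the primary test.

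**Working it through.** **Inputs from the plan.** Section 14.2: "The study is sized to achieve approximately 87% power to detect a hazard ratio (HR; TU-100 versus placebo) of 1.428 for GIR"; an "improvement in median time to GIR from 48 hours (2.0 days) for placebo (reference) to 34 hours (1.4 days) for TU-100"; and testing "at a 0.05 significance level of one-sided log-ranked test". The sample is 366 + 36 = 402, that is 122 evaluable and 134 enrolled per group. Section 14.5.2 supplies the t* rule and the 240 h limit.

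**The plan's own figure.** For one dose against placebo, with an event in each of 2 × 122 = 244 subjects, Schoenfeld's formula gives power = Φ(√(244/4) × ln 1.428 − 1.645) = Φ(2.783 − 1.645) = Φ(1.138) = 87.2%. This reproduces the stated 87%. A placebo median of 48 h with HR 1.428 gives 48/1.428 = 33.6 h under exponential times, which rounds to the stated 34 h.

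**How often is t* below 240 h?** The plan gives no survival shape. Take exponential times first.

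- Placebo: S(240) = 2^(−240/48) = 3.1%.
- TU-100: S(240) = 2^(−240 × 1.428/48) = 0.71%.
- Chance that an arm of 134 has at least one subject unrecovered at 240 h, 1 − (1 − S)^134: 98.6% for placebo, 61.5% for TU-100.
- t* = 240 h in one given comparison: 0.986 × 0.615 = 0.61.
- t* = 240 h in both: 0.986 × 0.615² = 0.37.

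**What is dropped.** If the active arm's last observation is a recovery at t* < 240 h, its Kaplan-Meier curve is zero from then on, so

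Δ(240) − Δ(t*) = ∫ from t* to 240 of S_placebo(u) du ≥ 0, where Δ is the placebo minus TU-100 RMST.

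The rule then understates the benefit. If placebo has the shorter maximum, the sign reverses, but both comparisons then share the same t*.

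**Simulation.** Three arms of 134, 2,000 trials per shape, placebo median 48 h, HR 1.428 for both doses. The shapes are assumptions. The 20 h shift reflects that subjects who have already met both recovery components cannot be randomized (Section 8.4). Without early loss:

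| Assumed shape | Median t* (h) | Horizons differ | Differ by > 10 h | Mean difference at t* | Mean difference at 240 h | Shortfall |
|---|---|---|---|---|---|---|
| Exponential | 240 | 64% | 49% | 18.5 h | 19.0 h | 0.5 h (3%) |
| Weibull 1.5 | 146 | 96% | 70% | 11.0 h | 11.7 h | 0.7 h (6%) |
| Weibull 2 | 110 | 96% | 52% | 8.0 h | 8.4 h | 0.4 h (5%) |
| Exponential shifted 20 h | 170 | 96% | 78% | 11.0 h | 12.0 h | 1.0 h (8%) |
| Weibull 0.8 shifted 20 h | 240 | 72% | 56% | 15.5 h | 16.1 h | 0.7 h (4%) |

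Means vary by a few tenths of an hour between runs. With 9% early loss the largest mean shortfall is 1.06 of 11.88 h (9%). In a single trial the 95th percentile of the shortfall is about 1.2 to 3.7 h. On average 2% to 3% of placebo subjects are still under observation past t*.

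**One dose effective, the other null.** The horizons differ in about 90% of trials for Weibull 1.5, Weibull 2 and the shifted exponential (median gaps about 28, 15 and 39 h), and in 48% for the shifted Weibull 0.8.

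**Neither dose effective.** With heavy tails (exponential, or shifted Weibull 0.8) the horizons differ in only 3% to 7% of trials. With the lighter tails they differ in roughly 60% to 67%, but the mean shift in the RMST difference is essentially zero.

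**The case against.** The rule is a fixed algorithm: the analyst has no discretion, and only its numerical value depends on the data. RMST is supportive, no decision rule uses it, and no dose-versus-dose contrast is planned. Quartiles and Kaplan-Meier medians also give effects in hours. Section 14.1 sends detail to a SAP that supersedes the protocol. No separate SAP text is in the document reviewed, so a fixed horizon there cannot be excluded. All of this stands, and it keeps the point small. It does not remove it: an algorithm can be fully specified and still leave the estimated quantity different from one comparison to the next.

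Several stronger readings are tempting and are not supported:

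- **The tail is always cut.** Under exponential times t* = 240 h in about 61% of trials for a given comparison, and nothing is lost.
- **Subjects with prolonged ileus are removed.** Everyone contributes up to t*; only later time is dropped, for a few percent of placebo subjects.
- **The doses cannot be compared.** Each difference from placebo is valid at its own t*; the two are merely not guaranteed a common window.
- **The loss is larger than shown.** Holding both medians (48 and 33.6 h) under Weibull 1.5 gives a median t* near 130 h and 15.3 versus 16.7 h (8% low), but that case implies HR = 1.428^1.5 = 1.71, not the protocol's 1.428.

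**Conclusion.** The point holds as one of prespecification and comparability in a supportive analysis. The horizon is data-driven and set for each pair, so the two windows may differ and late placebo time may be dropped. When the choice of horizon changes the estimate at HR 1.428, it usually understates the benefit, so it does not favour the drug. The mean shortfall is 0.4 to 1.1 h of a difference of about 8 to 19 h. Gaps of more than 10 h between the two horizons are common if both doses work (49% to 78% of trials across the assumed shapes) and rare with heavy tails and no effect.

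These sizes rest on assumed survival shapes, an assumed 0% or 9% early loss, and 134 subjects per arm. That the rule is pairwise and data-driven rests on the text alone. A reader might infer that the primary result is at risk. It is not: the Cox test does not use t*. Priority is low.

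**What to change.** State in the SAP, and align Section 14.5.2 and the Synopsis:

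1. For TGIR, t* = 240 h in both dose comparisons. If an arm's last observation is a recovery before 240 h, its Kaplan-Meier curve is zero from there and its RMST to 240 h is defined.
2. If any arm's last observation is censored before 240 h, use for both comparisons the smallest of the three arms' largest observed times. This is still data-driven, but common to both. With 9% assumed early loss it was triggered in 0.3% to 4% of simulated trials.
3. For each other time-to-event endpoint, name one common horizon once its censoring limit is set in the SAP. The 240 h limit is stated for TGIR only and should not be carried over by default.

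The cost is a few sentences before unblinding, with no new data or subjects. The downside is a slightly larger variance, because the sparse tail now counts.
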